6.7.4. Adverse events

Table 31 Summary of Adverse Events

		Experimental group (n=)		Control group (n=)		Total (n=)		
Item	Severity	Number of Incidence		NumberIncidence		NumberIncidence		P value
		OccurrencesubjectsRate (%)	Occurrenceof casesRate (%)	OccurrencesubjectsRate (%)	Occurrenceof casesRate (%)	OccurrencesubjectsRate (%)	Occurrenceof casesRate (%)	
Adverse events								
Severity		Mild						
adverse events								
Moderate		Severity						
Adverse Events								

		Experimental group (n=)		Control group (n=)		Total (n=)		
Item		Number		Number		Number		P value
		Occurrences	Incidence	Occurrences	Incidence	Occurrences	Incidence	
		subjects	Rate (%)	of cases	Rate (%)	of cases	Rate (%)	
Severe adverse events								
Adverse events related to the investigational device								
Adverse events related to surgery								
Adverse events leading to withdrawal								
Adverse events with a fatal outcome								

Note: Definition of adverse events related to the investigational device/procedure: Adverse events where the relationship to the investigational device/procedure is determined as "definitely related" or "possibly related".

Table 32 Event coding (SOC/PT)

		Experimental group (n=)		Control group (n=)		Total (n=)		
Indicator		Number		Number		Number		P value
		Occurrences	Incidence	Occurrences	Incidence	Occurrences	Incidence	
		subjects	Rate (%)	of cases	Rate (%)	of cases	Rate (%)	
All adverse events								
SOC1								
PT1								
PT2								
.....								

Table 33 Summary of Serious Adverse Events

		Experimental Group (n=)		Control Group (n=)		Total (n=)		
Item		Number		Number		Number		P value
		Occurrences	Incidence	Occurrences	Incidence	Occurrences	Incidence	
		subjects	Rate (%)	of cases	Rate (%)	of cases	Rate (%)	
All serious adverse events								
Trial Device-Related SAE								

Item	Experimental Group (n=)		Control Group (n=)		Total (n=)		P value
	Number of Occurrences	Incidence Rate (%)	Number of Occurrences	Incidence Rate (%)	Number of Occurrences	Incidence Rate (%)	
SAEs resulting in death							

Note: Definition of trial device-related serious adverse events: serious adverse events classified as "definitely related" or "possibly related" to the trial device.

Table 34 Serious Adverse Event Coding (SOC/PT)

Indicator	Experimental group (n=)		Control group (n=)		Total (n=)		P value
	Number of Occurrences	Incidence Rate (%)	Number of Occurrences	Incidence Rate (%)	Number of Occurrences	Incidence Rate (%)	
All serious adverse events							
SOC1							
PT1							
PT2							
.....							

6.7.5. Pre- and Postoperative Laboratory Tests Clinical Significance Cross-Tabulation

Table 35 Blood Count - Red Blood Cell Count

Group	Screening Period	Postoperative to discharge				Missing	Total
		Normal	Abnormal without clinical significance	Clinically Significant	Not Detected		
Experimental group	Normal						
	Abnormal without clinical significance						
	Clinically significant abnormality						
	Not tested						
	Missing						
Control group	Total						
	Normal						
	Abnormal without clinical significance						
	Clinically significant abnormality						
	Not tested						

Group	Screening Period	Postoperative to discharge					Total
		Normal	Abnormal without clinical significance	Clinically Significant	Not Detected	Missing	
	Abnormal without clinical significance						
	Clinically significant abnormality						
	Not tested						
	Missing						
	Total						

Table 36 Complete Blood Count - White Blood Cell Count

Table 37 Blood Count - Platelet Count

Table 38 Blood Routine - Haemoglobin

Table 39 Blood Biochemistry - Alanine Transaminase

Group	Screening Period	Postoperative to discharge					Total
		Normal	Abnormal without clinical significance	Clinically Significant	Not Tested	Missing	
Experimental group	Normal						
	Abnormal without clinical significance						
	Clinically significant abnormality						
	Not tested						
	Missing						
	Total						
Control group	Normal						
	Abnormal Non-clinically significant						
	Clinically significant abnormality						
	Not tested						
	Missing						
	Total						

Group	Screening Period	Postoperative to discharge						Total
		Normal	Clinically					
			Abnormal without clinical significance	Significant	Not			
				Abnormal	Tested	Missing		
Total								

Table 40 Blood Biochemistry - Aspartate Aminotransferase

Table 41 Blood Biochemistry - Serum Creatinine

Table 42 Blood Biochemistry - Total Cholesterol

Table 43 Blood Biochemistry - Triglycerides

Table 44 Blood Biochemistry - Low-Density Lipoprotein Cholesterol

Table 45 Blood Biochemistry - High-Density Lipoprotein Cholesterol

Table 46 Cardiac Enzymes Profile - Creatine Kinase

		48 hours post-operative					
Group	Screening Period	Normal	Abnormal without clinical significance	Clinically	Not	Missing	Total
				Significant Abnormal	Tested		
Experimental group	Normal						
	Abnormal without clinical significance						
	Clinically significant abnormality						
	Not tested						
	Missing						
	Total						
Control group	Normal						
	Abnormal without clinical significance						
	Clinically significant abnormality						
	Not tested						
	Missing						
	Total						

Table 47 Myocardial Enzyme Profile - Creatine Kinase Isoenzymes

Table 48 Cardiac Enzyme Profile - Troponin T

Table 49 Cardiac Enzyme Profile - Troponin I

Table 50 Twelve-lead electrocardiogram

Group	Screening Period	48 hours post-procedure					Total
		Normal	Abnormal without clinical significance	Clinically Significant Abnormality	Not Detected	Missing	
Experimental group	Normal						
	Abnormal without clinical significance						
	Clinically significant abnormality						
	Not tested						
	Missing						
	Total						
Control group	Normal						
	Abnormal without clinical significance						
	Clinically significant abnormality						
	Not tested						
	Missing						
	Total						

6.7.6. Device deficiency

Table 51 Device deficiency

Item	Indicator	Test group	Control Group	Total
Device deficiency	None n(%)			
	Yes n(%)			
	Total (Missing)			
	Statistic			
	P-value			

6.7.7. Intraoperative and Postoperative Vital Signs

Table 52 Vital signs during procedure

Table 53 Vital signs from post-procedure to discharge

6.8. QCA data analysis (FAS)

Table 54 Preprocedure QCA examination

Item	Indicator	Experimental Group	Control Group	Total
Preprocedure	N(Missing)			
Reference	Mean (SD)			
Vessel	Median			
Diameter	Q1, Q3			
(mm)	Min, Max			
	Statistic			
	P-value			
Preprocedure	N(Missing)			
diameter	Mean (SD)			
stenosis (%)	Median			
	Q1, Q3			
	Min, Max			
	Statistic			
	P-value			
Preprocedure	N (Missing)			
lesion length	Mean (SD)			
(mm)	Median			
	Q1, Q3			
	Min, Max			
	Statistic			
	P-value			

Table 55 Immediate QCA examination following scoring balloon angioplasty

Item	Indicator	Experimental Group	Control Group	Total
Intraballoon	N (Missing)			
minimum	Mean (SD)			
lumen	Median			
diameter (mm)	Q1, Q3			
	Min, Max			
	Statistic			

Item	Indicator	Experimental Group	Control Group	Total
Intraballoon Reference vessel diameter (mm)	P-value			
	N(Missing)			
	Mean (SD)			
	Median			
	Q1, Q3			
	Min, Max			
	Statistic			
Intraballoon residual stenosis (%)	P-value			
	N(Missing)			
	Mean (SD)			
	Median			
	Q1, Q3			
	Min, Max			
	Statistic			
	P-value			

Table 56 Postprocedure QCA examination

Item	Indicator	Experimental group	Control Group	Total
Minimal Lumen Diameter (mm)	N(Missing)			
	Mean (SD)			
	Median			
	Q1, Q3			
	Min, Max			
	Statistic			
	P-value			
Intra-device reference lumen diameter (mm)	N (Missing)			
	Mean (SD)			
	Median			
	Q1, Q3			
	Min, Max			
	Statistic			
	P-value			
Instrumental residual stenosis (%)	N (Missing)			
	Mean (SD)			
	Median			
	Q1, Q3			
	Min, Max			
	Statistic			
	P value			

Item	Indicator	Experimental group	Control Group	Total
Minimal	N (Missing)			
Lumen	Mean (SD)			
Diameter	Median			
within	Q1, Q3			
Segment (mm)	Min, Max			
	Statistic			
	P-value			
Intrasegmental	N (Missing)			
- Reference	Mean (SD)			
Lumen	Median			
Diameter	Q1, Q3			
(mm)	Min,Max			
	Statistic			
	P-value			
Intrasegmental	N(Missing)			
residual	Mean (SD)			
stenosis (%)	Median			
	Q1, Q3			
	Min, Max			
	Statistic			
	P-value			

Table 57 Acute lumen gain

7. List

See the appendix for the full list.

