1.5. Sample size

Based on literature review, clinical experience, and results from studies evaluating scoring balloon catheters for coronary artery disease, it is hypothesised that the study group's Sino scoring balloon dilation catheter will demonstrate comparable efficacy to the control group's Goodman coronary NSE balloon catheter, with an anticipated device success rate of 96%. Considering factors such as operator skill variation, lesion complexity, and subject comorbidities and disease severity, the sponsor, clinical experts, investigators, and statisticians jointly determined a non-inferiority margin Δ of -10%, a one-sided test α of 0.025, and a test power (1- β) of 0.8. PASS software calculations yielded a total sample size of 122 subjects, with 61 subjects in each group. Accounting for a 10% dropout rate, the trial requires 136 subjects, distributed as 68 in each group. The sample size calculation formula is as follows:

$$n_T = n_C = \frac{\left(Z_{1-\frac{\alpha}{2}} + Z_{1-\beta}\right)^2 [P_C(1 - P_C) + P_T(1 - P_T)]}{(|D| - \Delta)^2}$$

Where n_T and n_C denote the sample sizes for the treatment and control groups respectively, $Z_{1-\frac{\alpha}{2}}$ and $Z_{1-\beta}$ represent the quantiles of the standard normal distribution, P_T and P_C denote the expected event rates for the treatment and control groups respectively, $|D| = |P_T - P_C|$ denotes the absolute difference in expected rates between the two groups, and Δ denotes the non-inferiority margin, taken as a negative value.

This trial will be conducted concurrently across multiple clinical trial sites. In principle, enrolment numbers will be distributed as evenly as possible among centres to ensure adequate representativeness. However, considering feasibility and enrolment progress, adjustments to enrolment quotas for participating sites will be made based on actual circumstances, striving to maintain balanced enrolment scales across centres. The final enrolment size for any single centre shall not exceed 50% of the total number of cases.

2. Evaluation Criteria

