5.1. General Principles

Data description and analysis were performed using SAS software. All statistical tests employed two-sided significance testing (unless otherwise specified). Confidence intervals were calculated at the 95% confidence level.

1) Statistical Description: Quantitative indicators were described by calculating mean, standard deviation, median, minimum, maximum, lower quartile (Q1), and upper quartile (Q3). Categorical indicators were described by number and percentage of cases in each category. Grading indicators were described by number and percentage of cases in each grade.

2) Statistical inference: Comparisons between two groups will employ appropriate methods based on the nature of the indicator. For quantitative indicators, inter-group comparisons will utilise paired t-tests (assuming equal variance and normal distribution) or Wilcoxon signed-rank tests, depending on data distribution. Categorical indicators will be analysed using chi-square tests or exact probability methods (where chi-square is inappropriate). Ordinal data will be assessed via Wilcoxon signed-rank tests or the Mann-Whitney U test.

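### SAP 6.8 tests QCA minimal lumen diameter without baseline adjustment and leaves acute gain undefined, although pre-procedure vessel size and stenosis are already collected

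*SAP*

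**What the plan says.** SAP 6.8 holds four QCA tables on the FAS.

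- "Table 54 Preprocedure QCA examination" lists reference vessel diameter, percent diameter stenosis and lesion length. It has no row for pre-procedure minimal lumen diameter.
- Table 55 gives lumen diameter, reference diameter and residual stenosis right after the scoring balloon.
- Table 56 gives the same measures at the end of the procedure, once for the device length and once for the segment.
- "Table 57 Acute lumen gain" stands as a title only.

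In Tables 54 to 56 every variable carries a test statistic and a p-value. The rule behind them is SAP 5.1: "Comparisons between two groups will employ appropriate methods based on the nature of the indicator". For quantitative variables this means a t-test or a Wilcoxon test, with no covariate. SAP 5.1 names the paired and signed-rank versions, whereas protocol 6.4.2 names the two-sample versions. That discrepancy is a separate matter; I read both as unadjusted two-group tests.

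Protocol 5.6 leaves control of confounding as an option at the analysis stage, and protocol 6.4.2 allows further exploratory analyses. Neither names a model or a covariate. Lumen diameter and acute gain are not among the endpoints in SAP 2.1 and 2.2.

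**The concern.** Lumen diameter is reference diameter times (1 minus stenosis), so a 3.5 mm vessel ends with a larger lumen than a 2.0 mm vessel however well either balloon worked. An unadjusted test counts this spread as noise. A chance difference in vessel size between the arms then also shows up as a difference between devices.

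The primary endpoint is binary with high expected success. At 4% failure, 122 to 136 lesions (one per subject) give about 5 failures in all (122 × 0.04 = 4.9; 136 × 0.04 = 5.4). It therefore says little about how the two balloons compare in dilatation. The continuous QCA measures carry the finer evidence, and their p-values will be read that way.

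Acute gain has a further gap. Without a definition it is unclear which post-treatment lumen diameter is used (after the scoring balloon, in-device or in-segment), and the pre-procedure value it needs is not tabulated.

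**Working it through.** **1. The plan's own figure.** The only sample size stated is for the primary endpoint. Inputs from SAP 1.5: 96% success in both arms, margin -10%, and "a one-sided test α of 0.025, and a test power (1- β) of 0.8". With (1.96 + 0.842)² = 7.85:

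n = 7.85 × (2 × 0.96 × 0.04) / 0.10² = 7.85 × 0.0768 / 0.01 = 60.3, so 61 per arm; 61 / 0.9 = 67.8, so 68 per arm and 136 in total.

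Both results, before and after the dropout allowance, agree with SAP 1.5 ("PASS software calculations yielded a total sample size of 122 subjects, with 61 subjects in each group"). Nothing below changes them. No SD, correlation or power is stated for any QCA variable.

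**2. What adjustment buys.** The residual variance after adjustment is (1 - R²) × SD². At two-sided 0.05, 80% power and 68 lesions per arm (one each), the detectable difference in unadjusted SD units is

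(1.96 + 0.842) × √(2/68) × √(1 - R²) = 0.480 × √(1 - R²).

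| R² | Detectable difference (SD) | Equivalent unadjusted n per arm, 68/(1 - R²) |
|---|---|---|
| 0 | 0.480 | 68 |
| 0.1 | 0.456 | 76 |
| 0.3 | 0.402 | 97 |
| 0.5 | 0.340 | 136 |
| 0.75 | 0.240 | 272 |

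**3. Plausible R² for lumen diameter (all inputs assumed).** Let reference diameter R have mean 2.75 mm (midpoint of 2.0 to 3.5) and SD σR. Let residual stenosis have mean m and SD σs, independent of R. Then

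R² = (1 - m)²σR² / [(1 - m)²σR² + (2.75² + σR²)σs²].

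| Time point | m | σR (mm) | σs | R² |
|---|---|---|---|---|
| End of procedure | 0.15 | 0.25 | 0.14 | 0.0452 / (0.0452 + 0.1495) = 0.23 |
| End of procedure | 0.15 | 0.35 | 0.10 | 0.0885 / (0.0885 + 0.0769) = 0.54 |
| End of procedure | 0.15 | 0.43 | 0.08 | 0.1336 / (0.1336 + 0.0496) = 0.73 |
| After scoring balloon | 0.30 | 0.25 | 0.15 | 0.0306 / (0.0306 + 0.1716) = 0.15 |
| After scoring balloon | 0.30 | 0.43 | 0.12 | 0.0906 / (0.0906 + 0.1116) = 0.45 |

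Baseline measurement error of 0.2 mm multiplies R² by σR²/(σR² + 0.04): 0.61 at σR = 0.25, 0.75 at 0.35, 0.82 at 0.43. The fourth row then falls to about 0.09 and the second to about 0.40.

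**4. Simulation check.** A simulation of the same model truncated the values to the eligible range, used pre-procedure stenosis 72% (SD 8 or 12 points), and set baseline error at 0 or at 0.2 mm and 5 points. For end-of-procedure lumen diameter it gave 0.25 and 0.53 for the first two rows, or 0.15 and 0.39 with error. Values above 0.75 (up to 0.81 for lumen diameter and 0.84 for gain) arose only with a residual-stenosis SD of 6 points and no measurement error. Over its whole grid, gain ran from 0.22 to 0.84.

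**5. Residual percent stenosis.** It is already scaled to the vessel. R² is 0 if pre- and post-procedure stenosis are uncorrelated, and 0.3² = 0.09 if their correlation is 0.3.

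**6. Chance imbalance.** With σR of 0.35 to 0.43 mm, the difference in mean reference diameter between arms has SD σR × √(2/68) = 0.06 to 0.07 mm. Times 0.85, that moves mean final lumen diameter by about 0.05 to 0.06 mm.

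**The case against.** The strongest reply is that nothing decisive rests on these tables. Lumen diameter and gain are unpowered, supportive measures. Table 54 shows any imbalance in vessel size, and residual percent stenosis, which feeds the primary endpoint, needs no adjustment. All of that stands, and it keeps the point optional. Seeing an imbalance is still not the same as removing it from the estimate, and the protocol's general allowances name no model.

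A second reply is that Table 57 should not be faulted for a crude test. That is right. It specifies no comparison, and title-only shells occur elsewhere in this SAP (Tables 26-27 and 36-38, for example). The missing pre-procedure lumen diameter can also be derived from two variables in Table 54. What remains is that gain is not defined. Subtracting the baseline lumen does not remove vessel size either, since gain equals reference diameter times the drop in stenosis.

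A third reply is that Table 56 reflects the whole procedure. Protocol 5.5.3 allows stenting and post-dilation after the study balloon, so Table 55 is closer to the device effect. This stands: Table 55 must be covered, and R² may be lower there.

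A reader might go further and infer that the unadjusted tests discard half to three quarters of the available information. The documents do not support that. It amounts to assuming R² of 0.50 to 0.75, and they give no SD, correlation or R² for any QCA variable.

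**Conclusion.** The point holds as a modest efficiency gap. The plan names only unadjusted tests for QCA lumen diameter and does not define acute gain, while the covariates that would help are already collected. The precision forgone is the R² of those covariates: about 0.1 to 0.75 under the assumptions shown, with the low end for the post-scoring-balloon reading with measurement error and the high end for tight residual stenosis and exact measurement. The direction does not depend on the value; the size does, and it should always be quoted as an assumed range. The step from 0.48 to 0.40 or 0.34 SD assumes 68 independent lesions per arm. It would not be right to infer any effect on the primary non-inferiority conclusion, the sample size or residual percent stenosis.

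**What to change.** Add to SAP 6.8:

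- **Definitions.** Add pre-procedure minimal lumen diameter to Table 54, as reference diameter × (1 - percent stenosis). Define acute gain in Table 57 as post minus pre lumen diameter, and say which post-treatment reading is used.
- **Model.** For lumen diameter in Tables 55 and 56 and for gain in Table 57, report the arm difference with 95% CI from a linear model. Its terms are arm, pre-procedure core-laboratory reference diameter, pre-procedure percent stenosis and lesion type (de novo or restenotic).
- **Clustering.** Protocol 5.2.1 allows up to two lesions per subject, so use subject-clustered standard errors or a subject random effect.
- **Keep.** Retain the unadjusted summaries alongside. Residual percent stenosis may stay unadjusted.

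The cost is a few lines of SAP text and standard programming, with no new data. Protocol 6.4.7 permits recorded SAP changes before database lock, and the primary analysis is untouched.
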